My Surgical Success: A Randomized Controlled Pilot Study of a Pre-surgical Psychological Intervention

Statistical Analysis Plan

NCT03076190

June 15, 2018

Statistical Analysis

Statistical Analysis All analyses were conducted using SAS9.4. For acceptability and patient-reported outcomes, group differences were tested using analyses of varaiance (ANOVAs) for numerical covariates and chi-square tests for categorical covariates. The effect of the MSS vs HE control on opioid cessation in the 12-week postsurgical follow-up period was assessed using survival analyses. The opioid stop event was considered to have occurred if the patient reported an opioid stop date and was censored otherwise. Duration to opioid cessation was computed as days from surgery to the last patient-reported date of opioid stoppage or last known patient contact (for censored observations). Product-limit survival estimates (Kaplan-Meier curves) and the log-rank test of equality of survival curves between the MSS and HE control groups were generated using PROC LIFETEST. Time to opioid cessation event was assessed using a Cox proportional hazard regression model with the experimental condition as the predictor following a supremum test of the validity of the proportionality assumption (PROC PHREG). Two follow-up analyses were conducted. First, we tested whether MSS and HE control differed in the odds of postsurgical opioid cessation (independent of duration) using a logistic regression model (PROC LOGISTIC). Second, we tested whether the median time to opioid cessation was different between the two groups using a nonparametric test of medians (PROC NPAR1WAY with the median option). For each of the psychological covariates (pain catastrophizing, pain intensity, pain interference, anxiety, depression, and physical function), we assessed the treatment effect (MSS vs HE control) as follows. We first assessed whether there was evidence of a treatment time effect in the postsurgical period (two-, four-, eight-, and 12-week follow-up), and finding none, we averaged the postsurgical measures to create a composite postsurgical measure. For each of the covariates, we then specified a mixed-design ANOVA with treatment (MSS vs HE control, between-subjects), time (pre vs post, within-subjects), and the treatment time interaction as predictors.

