Power Analysis The study was designed to detect a hazard ratio of 1.9, the equivalent of a "medium" effect in terms of Cohen's d [23, 24], for the effect of the MSS treatment vs HE control in the 12-week postsurgical follow-up after surgery using Cox proportional hazards regression (PROC POWER). The analysis indicated that a total sample of 82 patients would be needed to yield a power of 0.8 and a two-tailed alpha of 0.05.

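### Averaging the week 2, 4, 8 and 12 symptom scores after checking only treatment-by-time makes a patient's composite depend on the visits completed, and can bias the arm comparison if completion differs between arms

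*SAP*

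**What the plan says.** The Statistical Analysis section of the SAP treats six outcomes alike: "pain catastrophizing, pain intensity, pain interference, anxiety, depression, and physical function". Its first step is a check over the four follow-up visits: "We first assessed whether there was evidence of a treatment time effect" "in the postsurgical period (two-, four-, eight-, and 12-week follow-up". The multiplication sign appears to have been lost in text extraction, so I read this as a treatment-by-time interaction, in line with the interaction named later in the section.

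The second step is the collapse: "finding none, we averaged the postsurgical measures to create a composite postsurgical measure". The composite is then the single postsurgical value in a "mixed-design ANOVA with treatment (MSS vs HE control, between-subjects), time (pre vs post, within-subjects" and their interaction as predictors.

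The SAP states no check for a change over time common to both arms. It does not say whether a patient with missed visits is averaged over the visits attended, handled in some other way, or excluded. It gives no attrition figure.

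**The concern.** A null treatment-by-time test shows at most that the arms run in parallel. It does not show that the course is flat. Week 2 is early recovery and week 12 is late, so pain intensity, pain interference and physical function could well shift in both arms between them. If they do, a patient seen only at weeks 2 and 4 gets an early-recovery mean, and a patient seen at all four visits gets a mean over the whole course.

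If one arm loses more patients early, that arm looks less recovered with no treatment effect at all. The error can run in either direction: it hides a benefit if MSS loses more, and exaggerates one if HE does. Restricting the composite to patients with all four visits avoids this under random loss, at the price of dropping everyone with a gap. All six symptom results pass through this one step.

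**Working it through.** **The plan's own figure.** The only design figure is the sample size: "a total sample of 82 patients would be needed". Freedman's formula gives (1.96 + 0.84)² × (1 + 1.9)² / (1.9 − 1)² = 7.85 × 10.38 = 81.5, so 82 events, which matches if every patient has the event. It concerns opioid cessation, not the composite. I use it only to set 41 per arm, assuming 1:1 allocation.

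**Assumptions not in the SAP.** Higher scores are worse. Means at weeks 2, 4, 8 and 12 are 1.0, 0.6, 0.2 and 0 SD in both arms (a 1 SD recovery). The correlation between any two scores, including the presurgical one, is 0.6. Loss is unrelated to outcome, and early leavers are split evenly between week 2 only and weeks 2 and 4 only.

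**Expected composite by visits attended**
- All four: (1.0 + 0.6 + 0.2 + 0)/4 = 0.45 SD
- Weeks 2 and 4: (1.0 + 0.6)/2 = 0.80 SD
- Week 2 only: 1.00 SD
- Average early leaver: (0.80 + 1.00)/2 = 0.90 SD, an excess of 0.90 − 0.45 = 0.45 SD

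**Bias with no treatment effect.** Bias = excess × difference in early-loss proportion.
- 30% vs 10% loss, 1 SD recovery: 0.45 × 0.20 = 0.09 SD
- 0.5 SD recovery: 0.225 × 0.20 = 0.045 SD
- 1.5 SD recovery: 0.675 × 0.20 = 0.135 SD
- 20% vs 20% loss, or no loss: 0
- 30% vs 10%, but those lost miss week 12 only: composite (1.0 + 0.6 + 0.2)/3 = 0.60, excess 0.15, bias 0.15 × 0.20 = 0.03 SD

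Subtracting the presurgical score leaves these biases unchanged, because that score does not depend on later attendance.

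**Rejection rates by simulation, no true effect.** The treatment-by-time test in a two-level pre/post ANOVA is equivalent to a t-test on composite minus presurgical score, so both forms were run.

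| Recovery | Early loss | Post composite | Change from pre |
|---|---|---|---|
| 0.5 SD | 30% / 10% | 5.5% | 5.6% |
| 1 SD | 30% / 10% | 7.4% | 8.1% |
| 1.5 SD | 30% / 10% | 10.0% | 11.6% |
| 1 SD | 20% / 20% | 5.0% | 4.9% |

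**Power for a true benefit of 0.5 SD, 1 SD recovery**

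| Analysis | MSS 30%, HE 10% | MSS 10%, HE 30% | 20% each |
|---|---|---|---|
| Plan's change contrast, available visits | 0.66 | 0.93 (inflated) | 0.83 |
| Change contrast, all four visits required | 0.79 | 0.78 | 0.80 |
| Visit-factor model, post scores only | 0.74 | 0.74 | 0.75 |
| Visit-factor model with pre score | 0.95 | 0.95 | 0.95 |

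The plan's contrast estimates a benefit of about 0.41 SD in the first column and 0.58 SD in the second, against a true 0.50. Requiring all four visits is unbiased here but keeps about 66 of 82 patients. Both models are unbiased. Their covariance was taken as known, so their power is slightly optimistic.

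**A heavier loss pattern.** With means of 1.0, 0.6, 0.3 and 0 and loss at each visit after week 2, week-12 completion of 42% vs 86% gives a bias of 0.17 SD (13% rejection on the post composite), and 34% vs 100% gives 0.25 SD (25%). At 61% in both arms the bias is about 0, but requiring all four visits keeps only about 50 of 82.

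**The case against.** The strongest reply is that nothing in the SAP shows the harm occurring. Bias needs both a common time trend and completion that differs between arms (or missingness tied to outcome). The SAP reports neither, and with complete visits the composite is sound. That stands, and it is why the point is conditional.

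A reader might take the censoring rule, "Duration to opioid cessation was computed as days from surgery to the last patient-reported date of opioid stoppage or last known patient contact", as evidence that missed questionnaires are expected. It is not. It is an ordinary rule for the opioid endpoint and also covers a patient followed to week 12 who is still taking opioids.

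A reader might also infer that a shared time trend by itself invalidates the average. It does not: an average over a common course is a legitimate summary when everyone contributes the same visits. Nor are available-visit averaging and complete cases the only options, since imputation or a minimum-visit rule could be used. The SAP names none of them.

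The pre/post contrast also softens the power loss. Ignoring the presurgical score gives a power of about 0.55 when MSS loses more; the plan's change contrast gives about 0.66. The bias itself is untouched.

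Finally, this is a pilot sized for opioid cessation, and a bias of 0.09 SD is about half the standard error of roughly 0.19 SD for the post composite. That limits the weight of the point. It does not remove it, because a better analysis of the same data is available.

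**Conclusion.** The concern holds in conditional form. The treatment-by-time check does not protect a per-patient average against a recovery trend shared by both arms, and the SAP does not fix how incomplete patients enter it. Where completion differs between arms, following the plan with available visits can shift the comparison by about 0.09 SD with 7-8% false positives (assumed 1 SD recovery, 30% vs 10% early loss, correlation 0.6), and by about 0.05 to 0.13 SD across recoveries of 0.5 to 1.5 SD. Loss confined to week 12 gives less, and heavier differential loss gives more. Equal random loss or complete visits give no bias. Requiring all four visits costs patients instead.

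The stronger statement, that the composite does bias the arm comparison, is not supported: the SAP gives neither attrition by arm nor a recovery course for any of the six outcomes. A trend is also more plausible for pain and function than for catastrophizing, anxiety or depression. The change is worth making but does not bear on the outcome for which the study was sized.

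**What to change.** For each of the six outcomes, replace the composite and the pre/post ANOVA with one repeated-measures mixed model (PROC MIXED) on all available postsurgical visits. Include visit as a categorical factor, treatment, treatment-by-visit, and the presurgical score, either as a covariate or as a baseline response with a mean common to both arms. State the within-patient covariance structure. Report the equally weighted mean of the four visit-specific treatment contrasts. With complete visits this targets the same average postsurgical effect as the composite. With missed visits, patients are compared at the visits they attended. The preliminary interaction check is then no longer needed to decide the analysis.

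The presurgical score must stay in. A post-only model has less power than the plan's own contrast under equal loss (0.75 vs 0.83 above). The gain to 0.95 comes largely from adjusting for that score and depends on the assumed correlation of 0.6.

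Cost: SAP wording and one model per outcome, with no extra patients or visits. The downsides are that a covariance structure has to be chosen and that validity rests on data being missing at random given what was observed. Completion by arm and visit should be reported alongside. If the composite is kept, the SAP should at least state how patients with missed visits enter it.

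### Six symptom outcomes: if the pre/post mixed ANOVA is read by its interaction term, it is an unadjusted change-score comparison; a baseline-adjusted sensitivity analysis would be at least as precise

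*SAP*

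**What the plan says.** The Statistical Analysis section of the SAP sets one procedure for six symptom scores: "pain catastrophizing, pain intensity, pain interference, anxiety, depression, and physical function), we assessed the treatment effect (MSS vs HE control) as follows".

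- Step 1 is a test across the postsurgical visits: "We first assessed whether there was evidence of a treatment time effect in the postsurgical period (two-, four-, eight-, and 12-week follow-up"). I read this as treatment-by-time, with a symbol lost in the text.
- Step 2 follows from its result: "finding none, we averaged the postsurgical measures to create a composite postsurgical measure".
- Step 3 is the model: "we then specified a mixed-design ANOVA with treatment (MSS vs HE control, between-subjects), time (pre vs post, within-subjects"), "and the treatment time interaction as predictors".

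The pre score therefore enters as one of two levels of the outcome; no adjustment for it as a covariate is stated. The section does not name which of the three terms is the treatment test. It does not say whether the pre score was taken before the intervention or only before surgery. It gives no SD or correlation for any score.

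The only sample-size figure is in the Power Analysis section: "a total sample of 82 patients would be needed to yield a power of 0.8". It concerns the Cox analysis of opioid cessation, not the symptom scores.

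**The concern.** With only two time levels, the treatment-by-time interaction asks whether mean change differs between arms. A change score subtracts the whole pre score, whatever its actual relation to the post score. Regression on the pre score estimates that relation and removes only what the pre score predicts. Where the two differ, the change score carries avoidable noise.

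At stake is precision in a small trial that calls itself "A Randomized Controlled Pilot Study of a Pre-surgical Psychological Intervention" and was not sized for these six outcomes. A symptom effect could be missed, or estimated with a needlessly wide interval, when the same data would give a sharper answer.

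A smaller point concerns the gate in front of the model. Averaging the four visits was made to follow from a non-significant test, and with 82 patients such a result does not show that the effect is constant.

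**Working it through.** **The plan's own figure.** For a hazard ratio of 1.9, two-sided alpha 0.05 and power 0.80, Freedman's formula gives (1.960 + 0.842)² × (2.9/0.9)² = 7.849 × 10.383 = 81.5, so 82 events. This matches the stated 82 if every patient has the event. It has no bearing on the symptom scores beyond supplying the sample size used below.

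**Equivalence.** The interaction contrast is (mean post − mean pre) in MSS minus the same difference in HE, which is the difference in mean change. In one simulated data set of 82 patients, the interaction F was 11.171 on 1 and 80 df, and the squared t for change was 11.171, with the same p of 0.00127. This holds for the interaction only. The treatment main effect averages pre and post and so halves the effect: for a true 0.5 SD effect its power is about 25 to 35% at correlations of 0.7 down to 0.3.

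**Inputs.** Total 82 (Power Analysis section) and four post visits (Statistical Analysis section). Assumed, because not given: 41 per arm, complete data, a pre SD of 1, a post SD of k at each visit, pre-post correlation q and visit-visit correlation r.

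**Formulae (per-patient variance).**
- Factor for the average of four visits: C = (1 + 3r)/4
- Change score: k²C + 1 − 2kq
- Adjusted for pre: k²(C − q²)
- Difference: (1 − kq)², which is never negative

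The direction therefore does not depend on the assumptions; the size does. The gain vanishes when kq = 1, that is, when the slope of post on pre is 1. Estimating that slope costs one degree of freedom.

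**Equal SDs (k = 1), q = r.** SE reduction = 1 − √(adjusted/change). Power for 0.4 SD = Φ(0.4/√(4v/82) − 1.96), with v the variance in the table.

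| Correlation | Change variance | Adjusted variance | SE reduction | Power, change | Power, adjusted |
|---|---|---|---|---|---|
| 0.3 | 0.875 | 0.385 | 34% | 0.49 | 0.83 |
| 0.5 | 0.625 | 0.375 | 23% | 0.63 | 0.84 |
| 0.7 | 0.375 | 0.285 | 13% | 0.84 | 0.92 |
| 0.8 | 0.250 | 0.210 | 8% | 0.95 | 0.98 |
| 0.9 | 0.125 | 0.115 | 4% | >0.99 | >0.99 |

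At 0.5, for example, the standard errors are √(4 × 0.625/82) = 0.175 and √(4 × 0.375/82) = 0.135. Simulation with the slope estimated (5,000 trials per case) gave SE reductions of 34/23/13/8/3%. Mean estimates were 0.396 to 0.403 for both methods, against a true 0.4.

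**Pre-post correlation below visit-visit correlation (k = 1).** With q = 0.3 and r = 0.7 the variances are 1.175 and 0.685: SE 24% smaller, power 0.39 against 0.59. With q = 0.5 and r = 0.8 they are 0.85 and 0.60: SE 16% smaller, power 0.50 against 0.65.

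**Unequal SDs, q = r.**

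| Correlation | k = 1.4: change / adjusted | SE reduction | k = 0.7: change / adjusted | SE reduction |
|---|---|---|---|---|
| 0.3 | 1.091 / 0.755 | 17% | 0.813 / 0.189 | 52% |
| 0.5 | 0.825 / 0.735 | 6% | 0.606 / 0.184 | 45% |
| 0.7 | 0.559 / 0.559 | 0% | 0.400 / 0.140 | 41% |
| 0.8 | 0.426 / 0.412 | 2% | 0.297 / 0.103 | 41% |

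**Pretest.** Noncentral F on 3 and 240 df, noncentrality = (sum of squared deviations from the mean effect) × 20.5/(1 − r), equal steps between visits. At r = 0.3/0.5/0.7/0.8, the power to detect an effect growing from 0 to 0.5 SD is 0.36/0.49/0.73/0.90. For one fading from 0.5 to 0.25 SD it is 0.12/0.15/0.22/0.32.

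**The case against.** The strongest reply is that nothing here is invalid. Under randomization with complete data and a pre-intervention score, the change-score comparison is unbiased, and the four-visit average is a legitimate target whether or not the effect varies. These are six outcomes on which the trial was not sized. All of this stands, and it limits the point to efficiency.

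The claim also depends on two facts that the SAP does not state: that the interaction is the tested term, and that the pre score precedes the intervention. The intervention is given before surgery, so a score taken before surgery could already be affected by it, and using that score as a covariate could mislead. Both objections stand, and the point is conditional on both facts.

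The equal-SD assumption matters too. A reader of the first table might infer that the loss is negligible once the correlation reaches 0.8. The document does not support that: with a post SD 0.7 times the pre SD, the gain at 0.8 is still 41%. Nor does it support a large gain: with a post SD 1.4 times the pre SD and a correlation of 0.7, there is none.

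The pretest criticism is largely moot for the reported contrast, because the remedy keeps the same week 2 to 12 average. The SAP does not claim to have shown a constant effect. What remains is that this average needs no significance test to justify it.

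What the reply does not remove is that adjustment uses scores already collected and cannot lose precision beyond one degree of freedom.

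**Conclusion.** The concern holds as a point about precision, at the level of something to consider. If the interaction is the treatment test, the specified analysis is an unadjusted change-score comparison and is never more precise than baseline adjustment, apart from one degree of freedom. With equal SDs the adjusted standard error is 4 to 34% smaller over correlations of 0.9 down to 0.3. Letting the post SD be 0.7 or 1.4 times the pre SD widens that range to between 0 and 52%. All figures assume 41 per arm and complete data, and no SD or correlation comes from the document, so the gain for any one outcome cannot be fixed from it.

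Three stronger readings are not supported. The symptom analysis is not shown to be biased. A non-significant pretest does not make the averaged contrast wrong. The opioid-cessation analysis, on which the 82 rests, is not touched.

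**What to change.** 1. State which term of the mixed ANOVA is the treatment test, and when the pre score was taken relative to the intervention.
2. If it was taken before the intervention, report for each of the six outcomes a baseline-adjusted comparison of the week 2 to 12 average. This can be an ANCOVA on the composite, or a mixed model of the four visits with treatment, visit, treatment-by-visit and the pre score as covariate, reporting the visit-averaged contrast with its confidence interval.
3. Label it a sensitivity analysis beside the existing one, because the SAP is written in the past tense and the pretest result is already known.
4. Report the visit average whatever the treatment-by-time test shows. Week-specific contrasts are optional and descriptive only.

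The cost is SAP wording and one extra model per outcome, six in all, on data already collected. The downside is that the analysis is post hoc. Week-specific contrasts, if shown, would add 6 × 4 = 24 estimates that are imprecise: with equal SDs, 95% half-widths of about 0.42/0.38/0.31/0.26 SD at correlations of 0.3/0.5/0.7/0.8. They should not be read as separate tests.

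### Does the power of 0.80 for 82 patients fail because the SAP gives no number of opioid-stop events?

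*SAP*

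**What the plan says.** The Power Analysis section sets the target effect: "The study was designed to detect a hazard ratio of 1.9", comparing MSS with HE control over 12 weeks after surgery. The model is Cox regression and the calculation was done in PROC POWER. The result is stated as follows: "The analysis indicated that a total sample of 82 patients would be needed to yield a power of 0.8", at a two-sided alpha of 0.05. The section gives no number of events, no expected share of patients who stop opioids, no allowance for loss to follow-up and no allocation ratio.

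The Statistical Analysis section defines the endpoint: "The opioid stop event was considered to have occurred if the patient reported an opioid stop date and was censored otherwise". Censored patients contribute time up to their last known contact. A follow-up logistic regression compares the groups on whether cessation occurred at all, ignoring its timing.

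**The concern.** In a time-to-event comparison the information comes from events, so a patient count fixes the power only together with an event fraction. The SAP states the first without the second. Its own endpoint rules allow for patients without an event, and the logistic model for cessation has content only if some patients do not stop.

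Freedman's formula for these inputs also returns 82 events. A reader could therefore suspect that an event count was reported as a patient count, with nothing allowed for censoring. If so, and if many patients were still taking opioids at 12 weeks or lost contact before reporting a stop, the power for a hazard ratio of 1.9 would be below the stated 0.80, and a null result would be less informative than the paragraph suggests.

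**Working it through.** **Inputs from the SAP, Power Analysis:** hazard ratio 1.9, two-sided alpha 0.05, power 0.80, N = 82. **Assumed:** 1:1 allocation, since no ratio is given. The event fraction is not given either, so it is varied.

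**Required events.** (1.960 + 0.8416)² = 7.849 and ln(1.9) = 0.6419.

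- Schoenfeld: 4 × 7.849 / 0.6419² = 76.2, rounded up to 77.
- Freedman: 7.849 × (2.9 / 0.9)² = 81.5, rounded up to 82.

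**Reproducing the 82.** There are two routes.

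- Schoenfeld with an event fraction: 76.21 / 0.93 = 81.9 and 76.21 / 0.94 = 81.1. Both round up to 82 patients.
- Freedman with every patient having an event: 81.5 rounds up to 82.

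The SAP does not show which route was taken. The first is an ordinary calculation with a small allowance for censoring.

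**Event fraction needed for 0.80 power.** Schoenfeld: 76.2 / 82 = 92.9%, or 77 / 82 = 93.9% after rounding up. Freedman: 81.5 / 82 = 99.4%.

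**Power at 82 patients.** With D events, power is Φ(√D × 0.6419 / 2 − 1.96) by Schoenfeld and Φ(√D × 0.9 / 2.9 − 1.96) by Freedman.

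| Share with an event | D | Schoenfeld | Freedman |
|---|---|---|---|
| 100% | 82.0 | 0.828 | 0.802 |
| 95% | 77.9 | 0.809 | 0.782 |
| 90% | 73.8 | 0.787 | 0.760 |
| 85% | 69.7 | 0.764 | 0.736 |
| 80% | 65.6 | 0.739 | 0.710 |
| 70% | 57.4 | 0.681 | 0.652 |

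**Which formula to trust.** The log-rank test was simulated with 41 patients per arm, exponential times, hazard ratio 1.9, censoring only at the end of follow-up and 20,000 runs per setting (standard error about 0.003).

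| Share with an event | Simulated power |
|---|---|
| 100% | 0.806 |
| 94% | 0.799 |
| 91% | 0.789 |
| 88% | 0.775 |
| 80% | 0.739 |
| 71% | 0.682 |

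With no censoring the simulation lies near Freedman. Once there is censoring it follows Schoenfeld. The supported threshold is therefore about 93 to 94%, and Freedman's near-100% requirement is too strict.

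**What 93% means by arm.** Under proportional hazards, the proportion not stopping in MSS is the HE proportion raised to the power 1.9. An overall 92.9% then corresponds to about 87.7% stopping in HE and 98.1% in MSS, with no early loss.

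**Allocation.** By Schoenfeld, 45:55 needs 77.0 events (94% of 82) and 40:60 needs 79.4 (97%). A 2:1 ratio would need 85.7, more than 82, but nothing in the SAP points to 2:1.

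**Is there a conflict inside the SAP?** The censoring rule and the logistic model show that non-events are possible, but they give no rate. By Schoenfeld, 5 patients without an event leave power at 0.804 and 6 leave it at 0.799. Five or six such patients among 82 are compatible with everything in the Statistical Analysis section.

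**The case for a change.** The strongest case for a change is that the missing input belongs to this very paragraph. The SAP makes a formal power claim, and the claim depends on a cessation rate that a reader cannot see. A rate of about 88% in HE and 98% in MSS by 12 weeks, with nobody lost early, is demanding and deserves to be stated. If the true rate were 80% overall, power would fall by about 6 points and the hazard ratio detectable with 80% power would rise to exp(2 × 2.8016 / √65.6) = 2.00. Stating the assumption would cost a sentence.

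Much of this stands. The power is conditional, the condition is not written down, and the arithmetic is right. What does not follow is that the figure is wrong or the trial underpowered. The lower fractions are illustrations, since the SAP gives no basis for 80% or 70%. Near the threshold the loss is slight: power stays within about 2 points of 0.80 down to roughly 88 to 89% events. Event-rate, loss and allocation assumptions are also commonly set out in the protocol, which is not available here, so their absence from a short SAP cannot be counted as an error.

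**Conclusion.** The concern does not call for a change. The figure of 82 can be reproduced by a standard route, and no statement in the SAP contradicts the event fraction which that route needs. With 1:1 allocation assumed, 82 patients give 0.80 power for a hazard ratio of 1.9 when about 93 to 94% have an observed stop (about 77 events). Power is about 0.79 at 90% and 0.74 at 80%. The gap is an unstated planning assumption, not a miscalculation.

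Filling it would also gain little. The SAP describes a pilot study and reports its analyses in the past tense, so the planned event fraction can no longer affect enrolment. The Kaplan-Meier, log-rank and Cox analyses would be the same whatever fraction was assumed, and the precision of the comparison now depends on the events actually observed. A reader who wants the design's power at another cessation rate can obtain it from the stated hazard ratio, alpha and sample size, as above, once an allocation ratio is assumed.

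This conclusion rests on allocation at or near 1:1 and on the absence of any document showing a materially lower cessation rate assumed at planning. Evidence of such a rate would reopen the question.
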